8.3 Statistical methods

Describe the statistical methods (or non-statistical methods of analysis) that will be employed.

Descriptive statistics will be calculated for all variables. Paired-samples t-tests (under intent to treat principles) will be used to test for differences from baseline-3 mos and 3-6 mos in motivation and physical activity (Aim 1) and fitness and vascular function (Aim 2). Given the lack of a control group, effect sizes (standardized mean differences) will be emphasized when interpreting data. Sensitivity analyses will be conducted using patients with/without radiation therapy.

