1.2 Primary Study Endpoints

State the primary endpoints to be measured in the study. Clinical trials typically have a primary objective or endpoint. Additional objectives and endpoints are secondary. The endpoints (or outcomes), determined for each study subject, are the quantitative measurements required by the objectives. Measuring the selected endpoints is the goal of a trial (examples: response rate and survival).

Change in total physical activity volume from baseline to 3 and 6 month as measured by the Actigraph GT3XP-BTLE (total activity counts).

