7.2.4 Lab Visit 2 (Month 3)

Three months following the baseline visit, participants will be asked to return to the lab to repeat measures taken during the baseline assessment. The researcher will remove the HeartPhone app from the participant's phone. Participants will be set up with an Actigraph accelerometer and given a 1-week wear log to record their activity for one week. Participants will then mail the accelerometer back at the end of the week.

A modification is proposed to include additional questions in the questionnaire pertaining to the acceptability of the Heartphone app. We will also engage in a brief semi-structured interview with the participants at this time to further gauge their experience using the HeartPhone app. The additional questions to be included in the questionnaire and semi-structured interview guide have been uploaded in the Other Attachments section of the Local Site Documents.

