7.2.5 Lab Visit 3 (Month 6)

Participants will then be asked to come back into the lab one final time approximately 6 months following their initial baseline visit. All measures taken at baseline and 3 months will again be taken at 6 months.

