8.2 Sample size determination

If applicable, provide a justification of the sample size outlined in section 8.1 – to include reflections on, or calculations of, the power of the study.

Assuming a 5% type-1 error rate, this sample size affords 80% power for detecting pre-post changes in the primary outcome of $d=0.47$ (one tailed)/ $d=0.53$ (two-tailed). Effect sizes for secondary outcomes will be used to inform planning for a future clinical trial.

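### The primary endpoint includes change from baseline to 6 months, but section 8.3 names tests only for baseline to 3 months and 3 to 6 months

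*Combined protocol and SAP*

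**What the plan says.** Section 1.2 gives the primary endpoint as "Change in total physical activity volume from baseline to 3 and 6 month as measured by the Actigraph GT3XP-BTLE (total activity counts"). The reference point is baseline for both times.

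Section 8.3 is the only analysis text. It states that "Paired-samples t-tests (under intent to treat principles) will be used to test for differences from baseline-3 mos and 3-6 mos" and applies this to differences "in motivation and physical activity (Aim 1) and fitness and vascular function (Aim 2"). Physical activity falls under Aim 1, so these are the tests for the primary outcome. The same section promises descriptive statistics for every variable and says that "effect sizes (standardized mean differences) will be emphasized when interpreting data". It names no comparison of baseline with 6 months, no repeated-measures model and no confidence interval.

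The month-6 data will exist. Section 7.2.5 says "All measures taken at baseline and 3 months will again be taken at 6 months". At the month-3 visit, section 7.2.4 says "The researcher will remove the HeartPhone app" and then "Participants will be set up with an Actigraph accelerometer and given a 1-week wear log to record their activity for one week". As written, the 3-to-6-month change therefore lies wholly after app removal.

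Section 8.2 states: "Assuming a 5% type-1 error rate, this sample size affords 80% power for detecting pre-post changes in the primary outcome", with d=0.47 one-tailed or d=0.53 two-tailed. It does not say which visit the change refers to.

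**The concern.** The endpoint section and the analysis section name different contrasts for month 6. Section 1.2 asks whether activity at 6 months differs from baseline. Section 8.3 asks whether it differs from month 3.

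The two questions can have opposite answers. If a month-3 gain is fully kept, the 3-to-6 change is expected to be zero while the baseline-to-6 change is positive. If the gain is fully lost, 3-to-6 shows a decline while the baseline-to-6 change is zero. A slow gain spread over both periods can miss significance in each step and still be clear over six months.

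What is at stake is a prespecified estimate, with its uncertainty, for one of the two time points in the primary endpoint. Without it, whether and how to report the 6-month change is left open until the results are known.

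**Working it through.** **Inputs.** N=30, 5% alpha, d=0.53 two-tailed and d=0.47 one-tailed (sections 8.1 and 8.2). The documents give no correlation between visits, no SD of change and no dropout allowance, so these are assumed and varied.

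**1. The plan's own figure.** For a paired t-test with n=30, the degrees of freedom are 29 and the noncentrality is d√30.
- Two-tailed: 0.53 × 5.477 = 2.90 against a critical t of 2.045, giving power 80.1%. The exact detectable d is 0.529.
- One-tailed: d=0.47 gives power 80.7%. The exact detectable d is 0.465.

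The stated figures reproduce for one contrast with 30 complete pairs.

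**2. The contrasts.** Write D03, D36 and D06 for the changes from baseline to 3, from 3 to 6 and from baseline to 6 months. Then D06 = D03 + D36, so with complete data the mean of D06 is the sum of the two planned mean changes. Its variance is Var(D03) + Var(D36) + 2 Cov(D03, D36). Two separate paired t-tests do not report the covariance.

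**3. Precision and power for baseline to 6 months.** Set both step-change SDs to 1 and let r be the correlation between the two steps. Then SD(D06) = √(2 + 2r). The 95% half-width is SD(D06) × 2.045/√30. The effective d for a fully kept gain is 0.53/SD(D06).

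| r (assumed) | SD(D06) | Half-width | Effective d | Power, 30 pairs | Power, 24 pairs (20% dropout, assumed) |
|---|---|---|---|---|---|
| -0.75 | 0.707 | 0.26 | 0.750 | 98% | 94% |
| -0.60 | 0.894 | 0.33 | 0.593 | 88% | 79% |
| -0.50 | 1.000 | 0.37 | 0.530 | 80% | 70% |
| -0.25 | 1.225 | 0.46 | 0.433 | 63% | 53% |
| -0.10 | 1.342 | 0.50 | 0.395 | 55% | 46% |

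The value r = -0.50 arises when all pairs of visits are equally correlated. The values -0.25 and -0.10 arise when correlation decays with time, with adjacent-visit correlation 0.5 or 0.8. Values below -0.50 arise if baseline and month 6 are more alike than adjacent visits.

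**4. What the two planned tests show together.** This was simulated with 30 complete pairs, a month-3 gain of 0.53, two-sided 5% tests and 100,000 trials per scenario. The table gives the chance that baseline-to-3 is significant and 3-to-6 is not.

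| r | Gain kept | Half lost | All lost |
|---|---|---|---|
| -0.75 | 77% | 52% | 8% |
| -0.50 | 77% | 53% | 11% |
| -0.25 | 76% | 55% | 14% |
| -0.10 | 76% | 56% | 15% |

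Taken alone, 3-to-6 is significant about 5% of the time if the gain is kept and about 80% if it is all lost. The pair of tests separates kept from fully lost, but not kept from half lost.

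**5. Two worked cases (step SDs of 1).**
- Steps of +0.30 and +0.30: each gives t = 0.30 × 5.477 = 1.64, not significant. Baseline-to-6 gives p = 0.003 at r = -0.5 and p = 0.027 at r = 0.
- Steps of +0.53 and -0.20: t = 2.90 (significant) and t = -1.10 (not significant). Baseline-to-6 gives p = 0.08 at r = -0.5 and p = 0.21 at r = 0.

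**6. False positives.** With no true change, the chance of at least one significant result at two-sided 5% is about 8 to 10% for the two planned tests, and about 12% if all three contrasts are tested without adjustment.

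**The case against.** The strongest reply is that little is really missing. Section 8.3 promises descriptive statistics for all variables, and the endpoint is itself a change. A mean, SD and count for the 6-month change would give its standard error. The investigators will hold each participant's values at all three visits, and the paired t-test is the only inferential method named, so there is little choice of method left. The study is uncontrolled, has 30 participants and puts effect sizes ahead of p-values.

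Much of this stands. A reader might infer that half of the primary endpoint goes unanalysed, or that no standard error could be had. The documents do not support that: the descriptive line may reach the 6-month change, and the data allow its standard error to be computed. What the line does not do is name that contrast, an interval or a test. Whether to report it remains open.

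A reader might also infer that the study is underpowered at 6 months. That does not follow either. Power is about 55% if correlation decays with time and about 98% if baseline and month 6 are strongly alike, and the documents do not say which applies.

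Section 1.2 could be read loosely as two successive intervals. Its wording measures change from baseline, no other section supports the looser reading, and even then the two sections would need to be aligned.

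**Conclusion.** The mismatch holds and does not depend on any assumed number: section 1.2 sets a baseline-to-6-month primary contrast, and section 8.3 names no test or interval for it. The 3-to-6 test answers a different question.

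The size does depend on assumptions: a month-3 gain of 0.53 change SDs, equal step SDs, 30 complete pairs, and a correlation between the two steps from -0.75 to -0.10. Under these, the pattern of an early gain with no significant later change is nearly as typical of half the gain being lost as of all of it being kept. The 95% half-width for baseline to 6 months is 0.26 to 0.50 month-3 change SDs.

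This should be fixed, but it is not a fatal flaw. It does not bias the planned tests or change N. Nor is the power statement in section 8.2 wrong, as a reader might infer: it is correct for a single contrast and simply does not say which one.

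**What to change.** In section 8.3, add a paired comparison of baseline with 6 months for the primary outcome, reported as mean change and standardized mean difference with a 95% confidence interval. Keep the 3-to-6-month test and label it a maintenance contrast.

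Rank the two primary contrasts: either test baseline to 3 months first and baseline to 6 months second, or state that baseline to 6 months is estimation only. In section 8.2, say that the 80% power (d=0.53 two-sided or d=0.47 one-sided) applies to one named contrast with 30 complete pairs, and say which sidedness will be used.

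The cost is one more analysis, with no new visits or measurements. Testing all three contrasts unadjusted would raise the chance of any false positive from about 8 to 10% to about 12%, which is why the ranking is needed. Testing in order keeps full alpha for baseline to 3 months, but a slow gain that misses at 3 months could not then be claimed at 6 months by a formal test. Splitting alpha equally instead would lower power at d=0.53 to 70.4% for each contrast, in units of that contrast's own change SD. Given the wide range of possible power, the 6-month interval should be read before its p-value.

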9.0 Confidentiality, Privacy and Data Management

For research being conducted at Penn State Hershey or by Penn State Hershey researchers only, the research data security and integrity plan is submitted using “HRP-598 – Research Data Plan Review Form Application Supplement”, which is available in the Library in CATS IRB (<http://irb.psu.edu>). Refer to Penn State College of Medicine IRB’s “Standard Operating Procedure Addendum: Security and Integrity of Human Research Data”, which is available on the IRB’s website. **In order to avoid redundancy, for this section state “See the Research Data Plan Review Form” in section 9.0 if you are conducting Penn State Hershey research and move on to section 10.**

For all other research, in the sections below, describe the steps that will be taken to secure the data during storage, use and transmission.

9.1 Confidentiality

9.1.1 Identifiers associated with data and/or specimens

List the identifiers that will be included or associated with the data and/or specimens in any way (e.g., names, addresses, telephone/fax numbers, email addresses, dates (date of birth, admission/discharge dates, etc.), medical record numbers, social security numbers, health plan beneficiary numbers, etc.).

If no identifiers will be included or associated with the data in any way, whether directly or indirectly, please indicate this instead.

Data collected from participants will be linked to each other by an alphanumeric code at the date that data collection begins. During data collection, the alphanumeric code will be temporarily linked with participants' names and email address for data management purposes but this key will be stored on a password-protected lab computer and destroyed at the end of data collection. The principal investigator will enter that code when initializing the app and Qualtrics survey during each visit.

9.1.1.1 Use of Codes, Master List

If identifiers will be associated with the data and/or specimens (as indicated in section 9.1.1 above), describe whether a master record or list containing a code (i.e., code number, pseudonyms) will be used to separate the data collected from identifiable information, where that master code list will be stored, who will have access to the master code list, and when it will be destroyed.

If identifiers are included or associated with the data as described in section 9.1.1 above, but no master record or list containing a code will be used, it will be assumed by the IRB that the investigator plans to directly link the identifiers with the data.

Alphanumeric codes matching the lab-generated email accounts will be used to identify participants (e.g., psuaim101). A master list containing the alphanumeric codes will be used to separate the data collected from identifiable information (the names, email addresses and phone numbers of the participants). This list that matches the names and contact information along with the code numbers will be stored in the locked file cabinet of the locked office of the research project manager (18A Rec Hall). Only the study team members responsible for consent and subject compliance monitoring calls will have access to that list. The list will be destroyed upon completion of the study.

9.1.2 Storage of Data and/or Specimens

Describe where, how and for how long the data (hardcopy (paper) and/or electronic data) and/or specimens will be stored. NOTE: Data can include paper files, data on the internet or websites, computer files, audio/video files, photographs, etc. and should be considered in the responses. Refer to the "Investigator Manual (HRP-103)" for information about how long research records must be stored following the completion of the research prior to completing this section. HRP-103 can be accessed by clicking the Library link in CATS IRB (<http://irb.psu.edu>).

Please review [Penn State's Data Categorization Project](#) for detailed information regarding the appropriate and allowable storage of research data collected according to [Penn State Policy](#)

[AD71](#). Although the IRB can impose greater confidentiality/security requirements (particularly for sensitive data), the IRB cannot approve storage of research data in any way or using any service that is not permissible by [Penn State Policy AD71](#).

Data from three cloud servers (a lab server for HeartPhone app data, Qualtrics server for questionnaire data, and the Fitabase server for the Fitbit data) will be linked in this study. Data collected from the HeartPhone application will be stored on the server while the study is in progress. This cloud-based dataset will include the serial number that will be given to each participant at the beginning of the study but no PHI. Data collected from Qualtrics questionnaires will be stored on Qualtrics' servers temporarily, and right after the study finishes they will be downloaded and stored on lab computers; data on Qualtrics' database will be then deleted from the Qualtrics' server. Data will be linked via the serial number which will be entered into the app and the Qualtrics questionnaire during the first lab visit by the principal investigator. As soon as data collection is completed, all data stored will be downloaded and deleted from the cloud servers. The integrated data file will be stored on a password protected computer in 17 Rec Hall (a locked room).

All data collected in Noll Lab is kept in the laboratory in locked cabinets, on a password-protected folder on the secured PSU server, and on password-protected computers maintained in a locked room. Only authorized personnel have access. Coded data shared with unauthorized persons cannot be traced to individuals. The list linking code numbers to participants is not shared with unauthorized persons and destroyed when project is completed and published.

Biological specimens are stored at University Park and Quest Labs, (Chantilly, VA). At University Park, the specimens are stored in a -80°C freezer in Noll first floor hallway. All specimens not exhausted upon analysis are maintained no longer than 5 years after publication.

9.1.3 Access to Data and/or Specimens

Identify who will have access to the data and/or specimens. This information should not conflict with information provided in section 9.1.1.1 regarding who has access to identifiable information, if applicable.

The principal investigators and approved research staff will have access to the data.

9.1.4 Transferring Data and/or Specimens

If the data and/or specimens will be transferred to and/or from outside collaborators, identify the collaborator to whom the data and/or specimens will be transferred and how the data and/or specimens will be transferred. This information should not conflict with information provided in section 9.1.1.1 regarding who has access to identifiable information, if applicable.

Some specimens are mailed or transported by lab members or couriers to outside labs for analysis. The outside labs are the Biomarker Core Lab (PSU, University Park) and Quest Diagnostics (Chantilly, VA). All specimens are coded and do not contain identifiers. We do not share the code with unauthorized persons.

9.2 Subject Privacy

This section must address subject privacy and NOT data confidentiality.

Indicate how the research team is permitted to access any sources of information about the subjects.

Describe the steps that will be taken to protect subjects' privacy interests. "Privacy interest" refers to a person's desire to place limits on whom they interact with or to whom they provide personal information.

Describe what steps you will take to make the subjects feel at ease with the research situation in terms of the questions being asked and the procedures being performed. "At ease" does not refer to physical discomfort, but the sense of intrusiveness a subject might experience in response to questions, examinations, and procedures.

During the lab visits, participants will complete an online questionnaire in the lab and a computer task. Participants will complete both the computer task and questionnaires in a private room in the lab without others present. Further, the exercise tests will be done in a private room in Noll Lab with only the investigator present. On occasion (e.g. educational visit, visiting colleague, site visit) participants may give permission for visitors to observe a procedure or experiment.

10.0 Data and Safety Monitoring Plan

This section is required when research involves more than Minimal Risk to subjects. As defined in "SOP: Definitions (HRP-001)", available in the Library in CATS IRB (<http://irb.psu.edu>), Minimal Risk is defined as the probability and magnitude of harm or discomfort anticipated in the research that are not greater in and of themselves than those ordinarily encountered in daily life or during the performance of routine physical or psychological examinations or tests. For research involving prisoners, Minimal Risk is the probability and magnitude of physical or psychological harm that is normally encountered in the daily lives, or in the routine medical, dental, or psychological examination of healthy persons. **Please complete the sections below if the research involves more than minimal risk to subjects OR indicate as not applicable.**

10.1 Periodic evaluation of data

Describe the plan to periodically evaluate the data collected regarding both harms and benefits to determine whether subjects remain safe.

Not applicable.

10.2 Data that are reviewed

Describe the data that are reviewed, including safety data, untoward events, and efficacy data.

Not applicable.

10.3 Method of collection of safety information

Describe the method by which the safety information will be collected (e.g., with case report forms, at study visits, by telephone calls and with subjects).

Not applicable.

10.4 Frequency of data collection

Describe the frequency of data collection, including when safety data collection starts.

Not applicable.

10.5 Individuals reviewing the data

Identify the individuals who will review the data. The plan might include establishing a data and safety monitoring committee and a plan for reporting data monitoring committee findings to the IRB and the sponsor.

Not applicable.

10.6 Frequency of review of cumulative data

Describe the frequency or periodicity of review of cumulative data.

Not applicable.

10.7 Statistical tests

Describe the statistical tests for analyzing the safety data to determine whether harms are occurring.

Not applicable.

10.8 Suspension of research

Describe any conditions that trigger an immediate suspension of research.

Not applicable.

11.0 Risks

List the reasonably foreseeable risks, discomforts, hazards, or inconveniences to the subjects related to the subjects' participation in the research. For each potential risk, describe the probability, magnitude, duration, and reversibility. Consider all types of risk including physical, psychological, social, legal, and economic risks. If applicable, indicate which procedures may have risks to the subjects that are currently unforeseeable. If applicable, indicate which procedures may have risks to an embryo or fetus should the subject be or become pregnant. If applicable, describe risks to others who are not subjects.

Please keep in mind that loss of confidentiality is a potential risk when conducting human subject research and should be addressed as such.

All downloaded data of the study will be stored on a password protected computer in 17 Rec Hall (a locked room) on the University Park campus, and only approved and trained personnel (research staff who completed the CITI training) will have access to the data. Thus, the loss of confidentiality may be minimized. Finally, participants are made aware that they can skip any question(s) they are not comfortable answering.

Physical discomfort may result from the aerobic tests performed in the study. It is possible that subjects may experience faintness, fatigue, muscle pain, chest pain, or a musculoskeletal injury during the exercise tests. These possible side effects are inherent in activities that require physical exertion. Study personnel will monitor subjects for the duration of the protocol and exercise will be submaximal to minimize risk. There is an AED in Noll Lab. In any emergency, 911 will be called immediately.

Further, discomfort arising from increasing physical activity is possible if participants rapidly increase their level of physical activity; however, any discomfort is expected to decrease as they adapt to the increased activity over the course of the study.

General note about the vascular function assessments: The research group's members administering the drugs and drawing blood are trained and competent in their duties. The group, led by [name], evaluates the effectiveness and safety of protocols and procedures in an ongoing fashion. They discuss the protocol with candidates, invite questions, and offer tours of the laboratory. Candidates read and sign informed consent forms detailing protocols, procedures, risks, sensations, compensation, etc. The researchers give candidates witnessed copies of the signed consent forms. After accepting participants into the study, the researchers discuss and review the procedures and protocols with them generally and at each step throughout the project. They frequently remind participants of the option to withdraw from the study at any time. Restricting access to

experiments, data, and coding to authorized personnel maintains confidentiality. The Noll Lab's electronics technician certifies the electrical devices for human use. Lists of emergency numbers remain by lab telephones. At least one cell phone is present at each experiment. A hospital and emergency medical services are within 1-2 miles of the lab. An AED hangs nearby in the hallway.

Microdialysis: The researchers insert a 25 g needle horizontally into and then out of the layers of the skin of the ventral forearm. The needle's entry and exit are about 2.5 cm (1 inch) apart. They thread the microdialysis "probe," comprising a tube of membrane (320 μm OD) with tubing attached at both ends (650 μm OD), through the needle. Then they withdraw the needle leaving the membrane under the skin. They perfuse the probe with sterile saline using a syringe pump.

Cutaneous microdialysis commonly causes some pain and bruising similar to that experienced during venipuncture. There is usually no pain after the probe is in place. The participant may experience mild pain while the researchers remove the probe. Minor bleeding may occur. As with routine venipuncture, a participant who is nervous about needles could have increased heart rate and blood pressure, become lightheaded or nauseated, or could faint.

As with venipuncture or any event that breaks the skin, infection is possible. However, no participants in any of the researchers' experiments have reported infection. The researchers place a sterile bandage on the site after the experiment. Although rare, if the membrane should break in half during removal, the researcher removes the remaining half by gently pulling the attached tubing. This presents no additional risk to the participant. In the unlikely event in which the membrane breaks during removal leaving an isolated piece of membrane under the skin, they treat the piece of membrane in a manner similar to that for a splinter in the skin. In this case, they have to make a superficial incision for removal.

Perfusate: Lactated Ringer's solution flows through the microdialysis probes. An allergic reaction to this physiological saline solution, although possible, is highly unlikely.

All substances added to the fluid perfusing the microdialysis probes (ACh, L-NAME, SNP) have been used previously clinically and/or in research in humans.

Microdialysis delivers small amounts of the substances to a nickel-sized area of the skin. The small quantities used and the extremely localized administration during microdialysis does not produce systemic effects. There are no reports of long- or short-term side effects of these substances administered through microdialysis. The chance of adverse reactions to these substances is extremely small given the minute amount delivered to a very small area of skin, the lack of adverse reactions to similar amounts delivered via MD in many other studies, and the lack of adverse effects in human cell cultures. There is a slight chance of allergic reaction to these substances that could produce redness, itching, rash, and/or swelling. A severe reaction (anaphylactic shock) could also cause fever, difficulty in breathing, changes in pulse, convulsions, and/or loss of consciousness.

The perfusate is sterile. The researchers prepare the perfusate in their laboratory using sterile techniques and supplies commonly used for this purpose in research laboratories. The Ringer's solution is sterile as purchased. They add other solutions aseptically to the sterile bag of Ringer's solution through 0.2 μm Gelman Sterile Acrodisc syringe filters. They mix the perfusate for same-day use and discard excess perfusate after the experiment. During the IND application process, the FDA accepted the researchers' technique for preparing perfusates. Although unlikely, in the case of a severe reaction to the perfusate, the researchers call 911.

Laser Doppler Flowmetry: The probe attaches to the skin with double-sided tape and measures skin blood flow in a 1 mm^3 volume of skin. Weak lasers can hurt the eye if one should stare into the light for a long time. The red light seen on the surface of the skin is harmless. The researchers do not turn on the laser until they tape the probes to a surface. They remove the tape afterward carefully. The researchers have used this technique in their lab with IRB approval for many years without incident.

Blood Pressure (manual, CardioCap 5): The manual method and CardioCap5 use a cuff that inflates on the upper arm. The cuff slowly deflates while the researchers listen to pulse-sounds at the inside of the elbow with a stethoscope, or the CardioCap 5 takes a measurement. The inflated cuff may make the arm feel tingly and numb, and the cuff may temporarily bruise the arm. Efficient and competent measurement technique minimizes the duration of cuff inflation. These techniques are unlikely to produce lasting ill effects.

Povidone Iodine: Hospitals and researchers use povidone iodine to clean and sterilize the skin. Participants could be allergic to iodine. An allergic reaction could cause redness, itching, rash, and/or swelling. A worse reaction could also cause fever, breathing problems, changes in pulse and/or blood pressure, convulsions, shock, and/or loss of consciousness. Staff use only alcohol on participants with iodine allergy as identified during screening.

Blood draw: Blood draws can cause anxiety (with increased heart rate and blood pressure), mild pain, swelling, nausea, lightheadedness, fainting, or bleeding. There is a slight chance of infection. A competent nurse performs blood draws using standard venipuncture procedure and techniques that minimize the chance of infection. Participants may recline for the procedure.

Tape and adhesive disks: Subjects could be sensitive to the adhesive of the tape and double-sided adhesive discs used in the study causing redness, rash, tenderness, and/or itching. The researchers remove the tape and adhesive discs carefully. Ointment is available, if needed.

ECG: The researchers attach three to twelve electrodes to the participant's chest and then attach the electrode wires to an ECG machine. The machine records the electrical activity of the heart. There are no adverse effects from this measure. A subject may be shy about electrodes applied to the chest. The staff carefully remove the tape afterward. They conduct the test professionally and privately.

Local Heating: The local heating control unit (Moor Instruments) precisely controls and monitors the temperature of the heated probe holders used with the laser Doppler flowmeter. To determine the maximal SkBF, the researchers increase the temperature of the heating units slowly (about 0.1°C every 1 second). The skin feels very warm but not painful. Local heating causes temporary redness of the skin that subsides within several hours. This technique is very unlikely to produce long-term ill effects. The local heating controllers (Moor Instruments) precisely control and monitor the temperature of the heated probe holders. The system has programmed maximal temperature limits. This technique is unlikely to cause long-term ill effects.

Latex: Some gloves and medical materials are made of latex rubber. Some people may be sensitive to latex. Screening identifies and excludes candidates having a known latex allergy.

Flow-mediated Vasodilation (FMD Test)/Doppler Ultrasound: There is a small chance the probe could irritate the skin. Placing the probe on the arm's skin may cause temporary minor redness. The inflated cuff may cause the participant's arm to feel numb or tingly, and the skin's color to change slightly. The cuff could cause mild bruising. The gel is the same as that used with medical ultrasound tests. The gel may feel cool or cold on the skin. A bad reaction to the gel is highly unlikely. The cuff inflates for a minimal amount of time. The temporary redness from the probe is unlikely to have lasting ill effects. The participant may decline the test.

